## 10.2 Procedures for Recording and Reporting Adverse Events

The Medicines for Human Use (Clinical Trials) Regulations 2004 and Amended Regulations 2006 gives the following definitions:

**Adverse Event (AE):** Any untoward medical occurrence in a participant to whom a medicinal product has been administered including occurrences which are not necessarily caused by or related to that product.

**Adverse Reaction (AR):** Any untoward and unintended response in a participant to an investigational medicinal product which is related to any dose administered to that participant.

**Unexpected Adverse Reaction (UAR):** An adverse reaction the nature and severity of which is not consistent with the information about the medicinal product in question set out in:

The summary of product characteristics (SmPC) for that product (for products with a marketing authorisation)

The Investigator's Brochure (IB) relating to the trial in question (for any other investigational product)

Serious adverse Event (SAE), Serious Adverse Reaction (SAR) or Unexpected Serious Adverse Reaction (USAR): Any adverse event, adverse reaction or unexpected adverse reaction, respectively, that

- Results in death;
- Is life-threatening;
- Required hospitalisation or prolongation of existing hospitalisation;
- · Results in persistent or significant disability or incapacity;
- Consists of a congenital anomaly or birth defect.

#### Important Medical Events (IME) & Pregnancy

Events that may not be immediately life-threatening or result in death or hospitalisation, but may jeopardise the patient or may require intervention to prevent one of the other outcomes listed in the definition above, should also be considered serious.

Although not a serious adverse event, any unplanned pregnancy should be reported via the SAE reporting system as stated below.

#### **Reporting Responsibilities**

King's College London & South London and Maudsley NHS Foundation Trust have delegated the delivery of the Co-sponsors' responsibility for Pharmacovigilance (as defined in Regulation 5 of the Medicines for Human Use (Clinical Trials) Regulations 2004 to the King's Health Partners Clinical Trials Office (KHP-CTO).

All SAEs, SARs and SUSARs will be reported immediately (and certainly no later than 24hrs) by the Investigator to the KHP-CTO and CI for review in accordance with the current Pharmacovigilance Policy.

The adverse event form (AEF) will be reviewed at each trial assessment clinic visit (thrice weekly during weeks 1-12), at the 16, 24 and 36 week follow-ups, and following any occurrences in between study visits and follow-ups. All clinical investigators in the study will be provided with full details of possible adverse medical events that may result from the trial medication and/or procedure, as well as other possible occurrences that may not be caused by or related to that product or procedure.

Any adverse events occurring during the trial will be recorded in the participant's source data worksheet and filed in their medical records at the end of the trial. They will also be transcribed on to

the electronic Case Record Form (eCRF). A decision and reporting flowchart will be developed for the management of adverse events, and all research workers and investigators will receive training on safety issues and notification procedures.

Clinicians will report, and the centre Principal Investigator (PI) will assess, each adverse event for seriousness, causality (relationship to trial IMP: definitely related, likely, possibly, unlikely or not related), expectedness, and intensity (mild, moderate and severe). Copies of any SUSAR (suspected unexpected serious adverse reaction) will be sent to the Chair of the DMC. The centre PI (or clinician delegated to undertake this task) will sign the SAE report form on paper. The Trial Manager will manage SAEs outside the eCRF in order to comply with KHP-CTO procedures. The KHP-CTO CRA will issue queries on the SAE during monitoring visits to collect follow-up information until resolution of the event, and basic event information will be entered on the eCRF.

The CI (or a doctor nominated by the CI) will review every event within one working day of the SAE form being received and determine whether the event was expected or unexpected. The CI may upgrade the intensity or causality of an event without the centre PI's agreement, but only the centre PI will be permitted to downgrade the event based on further follow-up information. If the clinical coordinators are unable to resolve any concern satisfactorily, collaborators, and all others associated with the study, will be instructed to write through the Trial Office to the Chair of the TSC, drawing attention to any concerns they may have about the possibility of particular side-effects, or of particular categories of patient requiring special study, or about any other matters thought relevant.

On a scheduled basis, the DMC will perform an integrated safety analysis of all adverse event information reported and ensure discussions are held and actions undertaken to secure the safety of all participants. If necessary, discussions may result in the trial's discontinuation. At the end of the fieldwork phase of the study each centre PI will write formally to the clinician assuming responsibility for the participants' ongoing clinical management, informing of them of any unresolved adverse events.

The KHP-CTO will report SUSARs to the regulatory authorities (MHRA, competent authorities of other EEA (European Economic Area) states in which the trial is taking place.

The Chief Investigator will report to the relevant ethics committee. Reporting timelines are as follows:

- SUSARs which are fatal or life threatening must be reported not later than 7 days after the sponsor is first aware of the reaction. Any additional relevant information must be reported within a further 8 days.
- SUSARs that are not fatal or life-threatening must be reported within 15 days of the sponsor first becoming aware of the reaction.
- KHP-CTO (on behalf of the co-sponsors), will submit a Development Safety Update Report (DSUR) relating to this trial IMP, to the MHRA and REC annually.

#### 10.3 Staff training

In accordance with high standards of research governance we will ensure that all researchers receive training in Good Clinical Practice (GCP). All staff employed on the grant and all investigators will be trained in GCP, use of the assessment tools, and trial standard operating procedures. Up-to-date CVs of all staff working on the trial will be kept in the Study Office, together with a log of all relevant training received by staff.

## 10.4 Treatment Stopping Rules

The trial may be prematurely discontinued by the Co-sponsors, Chief Investigator or Regulatory Authority on the basis of new safety information or for other reasons given by the Data Monitoring Committee / Trial Steering Committee regulatory authority or ethics committee concerned.

The trial may also be prematurely discontinued due to lack of recruitment or upon advice from a Trial Steering Committee (if applicable), who will advise on whether to continue or discontinue the study and make a recommendation to the sponsor. If the study is prematurely discontinued, active participants will be informed and no further participant data will be collected. The Competent Authority and Research Ethics Committee will be informed within 15 days of the early termination of the trial.

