It is possible that the NTX implant procedure will lead to local site infection or other complications. Prophylactic anti-biotic medication can be used post-surgery and participants will be monitored and checked by the trial nurse on each clinic visit and by each centre PI (physician) each month. Site inflammation will be man managed on a case-by-case basis, and likely to involve steroidal anti-inflammatory treatment. All serious and non-serious adverse events identified after randomisation until 16 weeks post-randomisation will be reported, irrespective of causality.

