### 25.2 Objectives

- To understand factors (patient, contextual and intervention related) that both facilitated and impeded the screening process of the NEAT trial
- To understand factors (patient, contextual and intervention related) that encouraged or discouraged patients from agreeing to participate in the NEAT trial
- To understand factors (patient, contextual and intervention related) that both facilitated and impeded progression from agreement to participate in the NEAT trial to actually joining the trial
- 4. To assess the treatment experiences of individuals who were accepted onto the NEAT trial but did not progress to join the trial

5. To assess the treatment experiences of all individuals who participated in the NEAT trial

- 6. To explore intended and unintended outcomes of participation in the NEAT trial
- 7. To ascertain the views and experiences of drug agency staff and research team members about the design and conduct of the NEAT trial
- 8. To ascertain the views of drug agency staff and research team members about how a future naltrexone trial should be designed and conducted
- 9. To assess whether the problems encountered were likely to be specific to naltrexone
- 10. To assess whether the problems encountered were likely to be specific to addiction trials

This follow-up has been designed to be incorporated into the NEAT trial over the period when it is being wound down. As a result, it is subject to a number of constraints. First, speed of data collection will be essential to ensuring that those involved in the NEAT trial can both be successfully located and recall sufficient information about the trial to enable meaningful analyses. Second, the small number of participants successfully recruited onto the trial (n=6) limits the scope of data collection. Third, time delays in securing NHS ethics approval could jeopardise the follow-up. For these practical reasons, it will be necessary to undertake a small exploratory follow-up study. Qualitative research, involving semi-structured interviews with a diverse range of individuals involved in the NEAT trial, provides an ideal method of generating the required data.

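### Section 10.4 stops all participant data collection on early closure, with no exception for safety data, and is not reconciled with the 16-week adverse-event window or SAE follow-up

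*Protocol*

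**What the plan says.** Protocol section 10.4 allows early discontinuation "on the basis of new safety information" or for other reasons, and adds that "The trial may also be prematurely discontinued due to lack of recruitment". It then says that on premature discontinuation "active participants will be informed and no further participant data will be collected". That sentence stands in the paragraph on recruitment but is worded for any early closure, and it carries no exception.

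Other sections of the same version (6.0) bear on this:

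- Section 10.1: "All serious and non-serious adverse events identified after randomisation until 16 weeks post-randomisation will be reported, irrespective of causality". The window is not made conditional on the trial staying open.
- Section 10.2, Reporting Responsibilities: the adverse event form is also reviewed "at the 16, 24 and 36 week follow-ups, and following any occurrences in between study visits and follow-ups". The monitor raises queries on each SAE "to collect follow-up information until resolution of the event". At the end of fieldwork each centre's investigator writes to the clinician taking over about adverse events still unresolved.
- Section 25, added after the decision of November 2016 to wind the trial down: interviews forming part of the trial, with an objective "To assess the treatment experiences of all individuals who participated in the NEAT trial". Section 25.3 plans to interview the six people who joined, and section 25.4 lists their experience of the closure as a topic.

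**The concern.** Site staff facing an early closure would find one section telling them to stop collecting participant data and others telling them to go on recording or following up safety events. Nothing says which prevails.

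The product makes this matter. The implant is a 90-day form (section 6.2), dissolves in the body and is not returned (section 6.7), so exposure does not end when the trial does. Section 10.1 itself has the participant card warn of overdose from attempts to overcome the blockade and of sensitivity to small opiate doses once naltrexone stops. Section 6.6 reports more implant-site events with active than with placebo implants (relative risk 4.68). It also warns that the published safety record may be biased because events in drop-outs are incompletely reported. A literal section 10.4 would introduce the same kind of gap into secondary objective D, which is to document safety. The rule would also apply when the trial closes because of a safety signal, which is when these data are needed most.

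By contrast, section 7.5 seeks continued follow-up, with permission, from participants who stop study drug only.

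**Working it through.** The protocol states no figure to reproduce. The check sets the provisions side by side and then counts days from the protocol's own durations.

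**Provisions compared**

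- *Section 10.4 against 10.1.* One stops participant data at closure. The other fixes a period counted from randomisation. For anyone randomised less than 16 weeks before closure, both cannot be followed as written. This is the direct conflict.
- *Section 10.4 against 10.2.* SAE follow-up works through monitor queries on events already reported, and the handover is a letter at the end of fieldwork. Both can need new information about a participant after closure, but neither promises continued participant visits. The conflict is real and less direct.
- *Section 10.4 against section 25.* The interviews collect new data from people who joined, after closure was decided and within the same protocol. No sentence exempts them.

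**Days falling after the data stop under a literal reading**

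Inputs: implant period 90 days (section 6.2); adverse-event window 16 × 7 = 112 days (section 10.1); implant at Day 0 of Study Week 1 (section 6.5.1). Assumption: randomisation and implant fall on about the same day. For closure at week w, implant days left = 90 − 7w and window days left = 112 − 7w.

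| Closure at week | Implant days left of 90 | Window days left of 112 |
|---|---|---|
| 1 | 90 − 7 = 83 | 112 − 7 = 105 |
| 4 | 90 − 28 = 62 | 112 − 28 = 84 |
| 8 | 90 − 56 = 34 | 112 − 56 = 56 |
| 12 | 90 − 84 = 6 | 112 − 84 = 28 |

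The week 1 row is close to the worst case. Closure before day 90 cuts into the implant period, and closure before day 112 cuts into the window. Active implants are in one arm of three, but the 16-week window covers every participant.

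**Did it matter in this trial?**

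Six people were recruited (section 25.2) and the wind-down was decided in November 2016. The protocol gives neither implant dates nor a date on which data collection stopped. Assuming no implant after 30 November 2016, the last 90-day period ended by about 28 February 2017 and the last 16-week window by about 22 March 2017. Both precede version 6.0, dated 20 June 2017. The 36-week follow-up (36 × 7 = 252 days) could have run to about 9 August 2017.

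**The case against.** The strongest reply is that section 10.4 is a special rule for a special case. Sections 10.1 and 10.2 describe a trial that is running, and on early closure the specific rule governs. Alternatively, participant data may mean routine research measures only. Both readings are possible, but the text states neither. The first would still end the 16-week window early, including in a closure for safety. The second is sensible and is what the fix would write down.

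Several further points stand and limit the finding.

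- A reader might infer that participants with active implants would be left with no safety data at all. The protocol does not support that. The SAE and SUSAR reporting duties and the handover of unresolved events are not expressly suspended, and participants carry a card with warnings and emergency unblinding details.
- A reader might infer that section 10.4 forbids the section 25 interviews. Section 25 is a later, specific addition with its own approvals, and 24 of its 30 planned interviewees never joined the trial (12 + 6 + 6). It needs an exemption line and no more.
- A reader might infer that safety data were lost because the trial did close. Nothing shows that adverse-event collection stopped. With six participants across three arms, objective D could not be answered meaningfully in any case, so truncated follow-up is not what defeats it.

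**Conclusion.** The point holds as a badly fixed rule. Section 10.4 is unqualified, it conflicts directly with the 16-week adverse-event window and less directly with SAE follow-up and handover, and no passage reconciles them. The size depends on when closure falls: from 83 implant days and 105 window days at week 1 down to 6 and 28 days at week 12. These figures assume a literal reading of section 10.4 and implantation at about randomisation. They measure what the rule would permit to go unrecorded; they are not an observed loss. Sample size, power and the primary analysis are unaffected. Severity is moderate: with six recruits and the windows probably elapsed before this version, practical exposure was small. The wording still matters for any closure under it and for the future implant trial that section 25.1 has in view.

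**What to change.** Reconcile section 10.4 with sections 10.1, 10.2 and 25 by changing the wording:

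1. Limit the data stop on early closure to recruitment and to efficacy or research measures.
2. State that the adverse-event recording and SAE follow-up already promised in sections 10.1 and 10.2 continue to their stated end for every participant already treated, whatever the reason for closure.
3. Add one line exempting the separately consented section 25 interviews.

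No dose or clinical rule changes. The cost is a small number of safety contacts after closure. Keeping the full thrice-weekly form review would be more: a participant one week in at closure would have 3 × 11 = 33 treatment-period visits left. Reduced, safety-only contacts would suffice, and section 10.4 should say if they replace the full schedule.

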## 11. Economic evaluation

Given that implanted XR-NTX is currently an unlicensed medication in Europe, and is more expensive than O-NTX, the relative cost-effectiveness of XR-NTX and O-NTX treatments will be assessed by including opportunity costs for stakeholders and comparing ratios of incremental opportunity costs (for all stakeholders) and incremental outcome (health related quality of life). Costs of the study interventions, external health services, and expenditure by the social and criminal justice sectors will be combined with the primary clinical outcome measure and quality adjusted life years to produce incremental ratios that will determine relative cost and cost-effectiveness.

Economic outcome assessments will be carried out after the 12-week treatment period and at the 36 week follow-up. The *a priori* primary economic outcome measure will be quality adjusted life years using the EQ-5D. The economic evaluation will take a broad policy perspective, including costs borne by hospital and community health and social services and the criminal justice sector, plus the costs of criminal activity. Detailed information on the resources associated with the treatments, including study medications, equipment, dispensing services, urine tests, nurse time, and contacts with key workers, medical, nurse and psychology staff, will be collected from clinical records. Resources external to the clinics, including staffed/supported accommodation, hospital contacts, community health and social services, criminal justice sector resources and crimes committed will be collected in interview with study participants at baseline, after the 12 week treatment period and at the week 36 follow up.

#### 11.1 Costs

Intervention costs will be calculated using a standard micro-costing (bottom-up) approach to incorporate the cost of all elements of the intervention (medications, equipment, dispensing services, urine tests and nurse time), plus appropriate clinic and managerial overheads. If relevant, adjustments will be made in sensitivity analysis to better reflect the long-term costs of the interventions in routine clinical practice. For example, this may involve assessment of potential changes to the supply and thus the cost of XR-NTX if demand in routine clinical practice is anticipated to increase as a result of the trial's conclusions. Costs for NHS hospital contacts will be taken from NHS reference costs. Nationally applicable unit costs will be applied to all community health and social care contact. Costs for contacts with the criminal justice system and for criminal activity will be drawn from Home Office estimates. These estimates are made up of three components: the costs in anticipation of crime; as a consequence of crime; and in response to crime.

## 11.2 Cost-effectiveness analysis

All economic analyses will be carried out on an intention-to-treat basis using a statistical analysis plan drawn up prior to the analysis of the data. Analyses will compare the cost and cost-effectiveness at the final 36 weekfollow-up of XR-NTX versus placebo and XR-NTX versus O-NTX, in line with the primary aims of the study. Additional analyses will explore XR-NTX versus O-NTX versus placebo in a three-way comparison. The primary analysis will explore cost-effectiveness in terms of quality adjusted life years to provide evidence suitable for comparison across disease areas. Secondary analysis will explore cost-effectiveness in terms of the primary clinical outcome measure as a check

on the results of the primary analysis. Cost-effectiveness will be assessed through the calculation of incremental cost-effectiveness ratios, defined as the additional costs of one intervention compared with another, divided by the additional effects of one intervention compared with another.

Uncertainty around the cost and effectiveness estimates will be represented by cost-effectiveness acceptability curves. A joint distribution of incremental mean costs and effects will be generated via bootstrapping to calculate the probability that each of the treatments is the optimal choice that a decision-maker might be willing to pay for a unit improvement in outcome.

Cost-effectiveness acceptability curves will be presented by plotting these probabilities for a range of possible values of the ceiling ratio. In addition, one-way sensitivity analysis will be used to explore the impact of hypothesized variations in the price of XR-NTX. It is anticipated that single imputation using multiple regression will be used for missing total cost data and last value carried forward conservatively employed for missing EQ-5D 5L data, since previous studies of this kind have demonstrated very low rates of missing data (around 5% of the sample in our group's trial of injectable diamorphine maintenance treatment). However, this assumption will be checked, and alternative methods employed, if necessary.

### 12. Statistics

The trial will be double blind. Active and placebo oral medication will be produced and encapsulated identically. Active and placebo implant devices will be produced and packaged identically. Clinicians and research workers completing baseline, clinic attendance assessments and all follow-ups will be blind to group allocation, as will patients and pharmacists. This design will ensure that the study has a high level of both treatment integrity (delivery of the treatment as intended) and treatment differentiation (treatment conditions differed from one another in the intended manner).

